#### **5.3.4 Handling of Withdrawals from Study Participation/Discontinuations of Study Treatment**

Subjects who withdraw from study participation, or are excluded from any efficacy endpoint analysis, or are lost to follow-up after signing the informed consent form (ICF), randomization, and receipt of the first dose of BPG will not be replaced. Subjects who withdraw consent after signing the ICF and randomization but before receipt of the first dose of BPG may be replaced.

If the subject requests to discontinue study treatment at any time after the first dose of BPG, the subject will be asked to continue scheduled study procedures including safety and efficacy evaluations, if possible, and be given appropriate care under medical supervision if symptoms of any AE related to participation in the study are continuing. The subject will be followed until the AE is resolved or until the subject's condition becomes stable.

Subjects who request to discontinue study treatment at any time after the first dose of BPG will be reminded of the importance of continuing in the study for safety evaluations. Subjects will be encouraged to complete the Early Termination Visit if they choose not to complete the remaining study visits (i.e., if they withdraw from study participation). The Early Termination Visit procedures are listed in Section 7.3. Subjects who choose to withdraw from study participation will no longer be contacted for follow-up.

In the case of subjects who fail to appear for a follow-up safety assessment, extensive effort (e.g., three documented contact attempts via phone calls, e-mails, etc., made on separate occasions and followed by a certified letter) will be made to locate or recall them, or at least to determine their health status. Subjects who cannot be located after extensive effort will no longer be contacted for follow-up. These efforts will be documented in the subject's records.

If a subject is withdrawn from the study due to an AE that prohibits continued participation in the study, s/he will be given appropriate care and treatment under medical supervision until the condition has resolved or becomes stable.

Safety and efficacy data will be collected on any subject who is excluded from any efficacy endpoint analysis. Refer to Section 11 for details on how subjects who are withdrawn will be handled during analysis.

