## 7.2 Follow-up

### 7.2.1 Visit 2 – Week 1 (Day 7 to 13)

- Subject will be evaluated for resolution of any clinical signs of infection and will be asked specific questions on medication tolerance. If the subject was not contacted following Visit 1, s/he will be evaluated for symptoms of a Jarisch-Herxheimer reaction at Visit 2 as described in Section 8.1.
- Medical history will be reviewed (including review of interval medical records and local laboratory results, if available) and updated as appropriate. If available in the medical record, the most recent viral load result since enrollment should be recorded. If the local laboratory results indicate a need for retreatment for syphilis infection, the subject will receive treatment according to the local clinic's standard protocols and will be withdrawn from the study per protocol Section 5.3.3.
- Interim sexual history since the last study visit will be collected. Specimens will be collected at sites of exposure for STI screening/diagnosis as indicated by local standard of care and subject history.

- 
- A urine pregnancy test will be performed on all subjects of childbearing potential.
  - All concomitant medications taken since the last study visit will be recorded on the appropriate data collection form. Previously recorded medications will be updated as appropriate.
  - A targeted physical examination will be performed by a qualified study clinician (including vital signs: temperature, heart rate, respiration rate, and blood pressure; and genital, rectal, oral, skin, and lymph node examinations).
  - Blood will be collected for follow-up RPR tests and storage.
  - Arm 2 only: second dose of BPG will be administered, and the subject will be observed per clinic SOP.
  - Study personnel will discuss with subjects and assess and record all AEs/SAEs (including solicited reactogenicity AEs and other unsolicited AEs).
  - Contact information will be reviewed, and the Week 2 visit will be scheduled.

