### **7.2.3 Visit 4 – Month 1 (Day 30 ± 7 days)**

- Medical history will be reviewed (including review of interval medical records and local laboratory results, if available) and updated as appropriate. If available in the medical record, the most recent viral load result since enrollment should be recorded. If the local laboratory results indicate a need for retreatment for syphilis infection, the subject will receive treatment according to the local clinic's standard protocols and will be withdrawn from the study per protocol Section 5.3.3.
- Interim sexual history since the last study visit will be collected. Specimens will be collected at sites of exposure for STI screening/diagnosis as indicated by local standard of care and subject history.
- A urine pregnancy test will be performed on all subjects of childbearing potential.
- All concomitant medications taken since the last study visit will be recorded on the appropriate data collection form. Previously recorded medications will be updated as appropriate.
- Study personnel will discuss with subjects and assess and record all AEs/SAEs (including solicited reactogenicity AEs and other unsolicited AEs).
- A targeted physical examination will be performed by a qualified study clinician (including vital signs: temperature, heart rate, respiration rate, and blood pressure; and genital, rectal, oral, skin, and lymph node examinations).
- Blood will be collected for follow-up RPR tests, storage, and CD4 counts on persons newly found to have HIV infection from Visit 1 to Visit 4 (inclusive) whose medical records do not include a CD4 count in the past 30 days. Clinicians will provide pre- and post-test counseling, treatment, and referrals per local standard of care.
- Contact information will be reviewed, and the Month 3 visit will be scheduled.

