### **7.2.5 Visit 6 – Month 6 (Day 180 ± 21 days)**

- Medical history will be reviewed (including review of interval medical records and local laboratory results, if available) and updated as appropriate. If the local laboratory results indicate a need for retreatment for syphilis infection, the subject will receive treatment according to the local clinic's standard protocols and will be withdrawn from the study per protocol Section 5.3.3.
- Interim sexual history since the last study visit will be collected. Specimens will be collected at sites of exposure for STI screening/diagnosis as indicated by local standard of care and subject history.
- A urine pregnancy test will be performed on all subjects of childbearing potential.
- All concomitant medications taken since the last study visit will be recorded on the appropriate data collection form. Previously recorded medications will be updated as appropriate.
- A targeted physical examination will be performed by a qualified study clinician (including vital signs: temperature, heart rate, respiration rate, and blood pressure; and genital, rectal, oral, skin, and lymph node examinations).
- HIV testing will be performed if the subject was previously noted to be HIV-uninfected.

Clinicians will provide pre- and post-test counseling, treatment, and referrals per local standard of care.

- Blood will be collected for follow-up RPR tests, storage, and CD4 counts on persons found to have HIV infection whose medical records do not include a CD4 count in the past 30 days.
- Contact information will be reviewed, and the Month 9 visit will be scheduled.

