## **9 ASSESSMENT OF SAFETY**

### **9.1 Specification of Safety Parameters**

Safety will be monitored throughout the study by physical examination (including vital signs: temperature, heart rate, respiration rate, and blood pressure; and genital, rectal, oral, skin, and lymph node examinations) and subject reporting. Safety will be assessed by the frequency and severity of AEs/SAEs (including solicited reactogenicity AEs and other unsolicited AEs) occurring from the time of study product administration through the Month 1 visit.

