### 11.4.4 Efficacy Analysis Plan

#### 11.4.4.1 Primary Efficacy Analysis

For the primary analysis, serological response to therapy by Month 6 will be defined as follows:

- 4-fold or greater decline in RPR titer by Month 6 compared to baseline, OR
- RPR-negative by Month 6 (i.e., seroreversion).

For the primary analysis, subjects who do not meet either of the above criteria by Month 6 will be classified as not experiencing serological response. If a subject has an observed serological response prior to meeting one of the Evaluable analysis population exclusion criteria, the subject will be included in the analyses as a responder. For subjects who have received BPG through the study and subsequently require retreatment for syphilis infection (i.e., per the local clinic's standard protocols), data collected following retreatment will not be used for analyses. Exploratory analyses of the primary outcome will consider alternative classifications of subjects (see Section 11.4.4.2).

For the comparison of efficacy of one dose versus three doses of BPG 2.4 MU, the number and proportion of subjects with serological response will be summarized overall and by treatment.

The point estimates for the treatment-specific proportions and difference in proportions as well as corresponding 95% confidence intervals will be reported. A hypothesis test will be conducted using the Farrington-Manning test at the 5% one-sided level of significance to formally compare the treatment arms. The primary analysis will be performed in the ITT analysis population and repeated as a secondary analysis in the mITT and the Evaluable analysis populations.

As the ITT analyses will include subjects who may not have adequate serological data to determine their response status for any reason, the response will need to be imputed. Multiple methods for imputation will be explored (e.g., Last Observation Carried Forward); details will be provided in the Statistical Analysis Plan.

As a secondary corroborative analysis, the Cochran-Mantel-Haenszel Chi-square test will be used to compare the two treatment arms with respect to response rate across HIV status subgroups (HIV-infected, HIV-uninfected). The Breslow-Day test for the homogeneity of odds ratios will be used to determine if the difference between the two treatment groups with respect to response rates varies by HIV status.

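### A failed search for a missing subject ends contact for good, with no new attempt provided for when the Month 6 visit falls due

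*Protocol*

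**What the plan says.** Protocol section 5.3.4 sets a trigger, a search and a consequence.

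- Trigger and search: "In the case of subjects who fail to appear for a follow-up safety assessment, extensive effort" is made to find or recall them, or at least to learn their health status. The example given is "three documented contact attempts via phone calls, e-mails, etc., made on separate occasions and followed by a certified letter".
- Consequence: "Subjects who cannot be located after extensive effort will no longer be contacted for follow-up".

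The same section ends contact in the same way for subjects who choose to leave the study. For contact purposes, an unlocated subject is therefore treated like one who has withdrawn.

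Section 11.4.4.1 places the primary analysis in the ITT population, which section 11.4.1 defines as everyone randomized. It foresees gaps: "As the ITT analyses will include subjects who may not have adequate serological data to determine their response status for any reason", their response is to be imputed, with details left to the SAP. The same section also classes subjects who have not met a response criterion by Month 6 as not having responded. RPR blood is drawn at every scheduled visit (section 4, Appendix A).

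**The concern.** The rule makes one unsuccessful search final. It applies to subjects who have not withdrawn consent, and it can take effect in the first weeks of a 12-month follow-up. The outcome that decides the trial is read up to Month 6. A subject who cannot be found in Week 2 may be reachable by Month 3 or Month 6, but the protocol directs sites not to try.

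At stake are avoidable missing titers in the primary analysis. In a noninferiority trial with a 10-point margin these matter, because the result then depends partly on how undetermined responses are filled in. An analysis plan can choose an imputation method; it cannot supply a titer that was never drawn.

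**Working it through.** **The plan's own figures.** They reproduce and are not in dispute.

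- Evaluable size, from section 11.2 (response 0.788 in both arms, margin 0.10, one-sided 0.05, 80% power): n per arm = (1.645 + 0.842)² × 2 × 0.788 × 0.212 / 0.10² ≈ 207, against the stated 210. Exact enumeration of the Farrington-Manning test at 210 per arm gives power 0.804.
- Enrollment: 420 / (1 − 0.25) = 560, as stated.

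**How early contact can end.** The inputs are the visit windows in sections 7.2.1 to 7.2.5. The Month 6 visit is Day 180 ± 21, so Day 159 to 201. Visit 3 is 6 to 12 days after Visit 2, so Day 7 + 6 = 13 to Day 13 + 12 = 25. Shortest gap = 159 − last day of the missed window. Longest gap = 201 − first day of the missed window.

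| Missed visit | Window (day) | Shortest gap | Longest gap | Post-baseline draws in hand if earlier visits were kept |
|---|---|---|---|---|
| Visit 2, Week 1 | 7–13 | 159 − 13 = 146 | 201 − 7 = 194 | 0 |
| Visit 3, Week 2 | 13–25 | 159 − 25 = 134 | 201 − 13 = 188 | 1 |
| Visit 4, Month 1 | 23–37 | 159 − 37 = 122 | 201 − 23 = 178 | 2 |
| Visit 5, Month 3 | 69–111 | 159 − 111 = 48 | 201 − 69 = 132 | 3 |

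The gaps are counted in days from the missed visit. The search takes some time that the protocol does not fix, so the actual interval is somewhat shorter.

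**Who is affected.** Response counts if seen at any draw up to Month 6. The outcome is therefore left open only for subjects with no response recorded before loss. After a miss at Visit 2 there is no scheduled post-baseline draw, so no response can have been seen at one. After a later miss, some subjects will already be responders.

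**Is there a second attempt anywhere?** Sections 5.3.4, 7.2 and 7.3 and Appendix A were read for one. Contact details are reviewed and the next visit booked at each attended visit, but no text tells a site to try an unlocated subject again when a later window opens.

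**The case against.** The best reply is that the rule is milder than it looks. Contact stops only after a substantial, documented effort, and the three attempts plus letter are an example, not a ceiling. The subject is not withdrawn and may come back. Responses already observed are kept. Section 7 refers further visit instructions to the Manual of Procedures, which might add re-contact. All of this limits the reach of the rule but does not supply a renewed attempt, and a manual that did so would contradict the protocol sentence.

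Four stronger readings are tempting, and the documents do not support them.

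- *The search duty ends at Month 1.* A reader might infer this from section 9.1, where the AEs and SAEs assessed are those "occurring from the time of study product administration through the Month 1 visit". But the same section opens by saying that safety is monitored by examination for the whole study, and the Protocol Summary gives safety as one purpose of the visits up to Month 12. The trigger wording is loose rather than clearly limited to Month 1.
- *Every unlocated subject must be imputed.* This is not so, because of the response-by-Month-6 definition.
- *The 25% allowance measures the loss.* Section 11.2 describes it as subjects ineligible for the primary analysis. The Evaluable exclusions in section 11.4.1 include ineligibility at baseline, TPPA result, HIV status, incomplete dosing and other antibiotics. Power or error rates computed from 25% missing would describe total assumed missingness, not the effect of this rule.
- *The rule favors a false noninferiority claim.* Visits 2 and 3 carry a dose only in Arm 2, so Arm 1 subjects may have less reason to attend. If that left more Arm 1 outcomes missing and scored as non-response, noninferiority would become harder to show, not easier. The protocol gives no figure for either arm.

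**Conclusion.** The point holds as a weakness in a stated rule, not as a contradiction or a wrong figure. Section 5.3.4 ends outgoing contact permanently after one failed search, without withdrawal of consent, and no later attempt is provided for. Contact can end about 146 to 194 days before the Month 6 visit after a miss at Week 1, and about 122 to 178 days before it after a miss at Month 1. Subjects with no response already observed may then have a primary outcome that has to be imputed or scored as non-response in the ITT analysis.

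The number of such subjects is not in the documents, nor is the share who could be reached later, so no loss of power or inflation of error can be put on this rule alone. The conclusion rests on reading the sentence as written, and on the assumption that at least some subjects who cannot be found early could be found later. It is a cheap improvement worth making.

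**What to change.** In Protocol section 5.3.4, replace the sentence that stops contact with:

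*An unsuccessful search closes that visit only; unless consent has been withdrawn, contact is attempted again when each later visit window opens, at minimum Month 3, Month 6 and Month 12.*

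In the preceding sentence, make clear that the search applies to any missed visit with an RPR draw (Visits 2 to 8), which removes the doubt over what counts as a safety assessment.

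The cost is a wording change and a few extra calls, texts, emails or letters per unlocated subject. Some will fail, and all must stay within the methods the local IRB allows; section 5 already foresees such contact to support retention. No visit is added. Nothing further is needed for subjects who choose to withdraw, because they are already encouraged to complete the Early Termination Visit, which includes an RPR titer.

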### **5.3.5 Termination of Study**

Although the study sponsor has every intention of completing the study, the sponsor reserves the right to terminate the study at any time for clinical or administrative reasons. Reasons for termination include, but are not limited to, study closure due to DSMB review and recommendation or at the discretion of DMID.

---

## 6 STUDY INTERVENTION/INVESTIGATIONAL PRODUCT

### 6.1 Study Product Description

Penicillin G benzathine injectable suspension (BPG) is prepared by the reaction of dibenzylethylene diamine with two molecules of penicillin G. It occurs as a white crystalline powder and is very slightly soluble in water and sparingly soluble in alcohol. BPG (Bicillin® L-A) is available as a suspension for deep intramuscular (IM) injection.

#### 6.1.1 Acquisition

BPG (Bicillin® L-A) is manufactured by Pfizer Laboratories and will be purchased from the study budget. Upon request by DMID, BPG will be transferred to:

DMID Clinical Materials Services (CMS)  
Fisher BioServices  
[name]  
[name]  
Phone: 240-  
Fax: 240-

BPG will be shipped from the DMID Clinical Materials Services (CMS) to the investigational sites upon request and approval by DMID.

#### 6.1.2 Formulation, Packaging, and Labeling

BPG contains penicillin G benzathine in aqueous suspension with sodium citrate buffer and, as weight/volume, approximately 0.5% lecithin, 0.6% carboxymethylcellulose, 0.6% povidone, 0.1% methylparaben, and 0.01% propylparaben. Bicillin® L-A suspension in the disposable-syringe formulation is viscous and opaque, and is available in a 2-mL size containing 1.2 MU BPG per syringe. It is labeled for deep **IM injection only**, not for intravenous (IV) use.

#### 6.1.3 Product Storage and Stability

Refer to the protocol-specific MOP for guidance on BPG storage.

### 6.2 Dosage, Preparation, and Administration of Study Intervention/Investigational Product

At each site, a Research Pharmacist or clinician may be delegated the responsibility of BPG dispensation. The Research Pharmacist must be a licensed, registered pharmacist and is the

---

preferred healthcare practitioner to be delegated to perform this activity. If a Research Pharmacist is not available, a physician, nurse practitioner, physician assistant, registered nurse, or other authorized healthcare practitioner who is a member of the clinical study staff may be delegated to dispense BPG. These personnel must be licensed, trained, and qualified to prepare an investigational study product and must be authorized to dispense it under state and local rules and regulations.

BPG will be administered as a deep IM injection in the upper, outer quadrant of the buttock. Subjects will be randomized to one of two treatment assignments:

- Arm 1: BPG 2.4 MU injected once as two 2-mL injections (one in each buttock)
- Arm 2: BPG 2.4 MU injected weekly as two 2-mL injections (one in each buttock) for three successive weeks

### **6.3 Accountability Procedures for the Study Intervention/Investigational Product(s)**

After receiving the BPG, the site principal investigator (PI) is responsible for its distribution and disposition and has ultimate responsibility for its accountability. The site PI may delegate to a site Research Pharmacist or an appropriately qualified staff member the responsibility for BPG accountability. The designee will be responsible for maintaining complete records and documentation of BPG receipt, accountability, dispensation, temperature and storage conditions, and final disposition. All BPG, whether administered or not, must be documented on the appropriate study drug accountability record or dispensing log. The sponsor's monitoring staff will verify the participating clinical sites' study drug accountability records and dispensing logs per the study monitoring plan.

Upon completion or termination of the study and after the final monitoring visit, final disposition of the unused BPG will be determined by DMID and communicated to the sites by the DMID Clinical Project Manager.

### **6.4 Assessment of Subject Compliance with Study Intervention/Investigational Product**

All BPG injections will be directly observed by the administering clinician. Compliance with study product for all subjects will be defined as whether subjects receive all assigned doses within the assigned visit windows.

## **6.5 Concomitant Medications/Treatments**

Administration of any medications, therapies, or vaccines will be recorded on the appropriate data collection form. Concomitant medications will include all medications taken 30 days before initiating study treatment through Month 12 or early termination, whichever occurs first. Prescription and over-the-counter drugs will be included, as well as herbs, vitamins, and supplements. Previously recorded medications will be updated as appropriate.

Subjects who have received BPG and are subsequently diagnosed with a concomitant infection that requires systemic antibiotics will receive treatment according to the local clinic's standard protocols. Likewise, subjects who have received BPG through the study and subsequently require retreatment for syphilis infection will receive treatment according to the local clinic's standard protocols and will be withdrawn from the study per protocol Section 5.3.3.

At the discretion of the site PI, use of new medication should prompt evaluation for the presence of a new diagnosis of chronic medical disease or condition.

Medications that might interfere with the evaluation of BPG should not be used unless absolutely necessary.

Refer to Section 5 (Subject Inclusion and Exclusion Criteria) for medications that are prohibited for study eligibility and throughout study participation.

---

